## 8.2. Follow-up

For prevalence estimations of individuals with recorded immunoglobulin prescriptions among the general study population (*objective 1*), individuals present in the data source between 1st of January 2017 and 31st of December 2024 will be included. For prevalence estimations among immunoglobulin users (*objective 2*), follow up will start on date of immunoglobulin prescription during the study period.

For patient-level drug utilisation (*objective 3*) and characterisation of individuals initiating immunoglobulin treatment (*objective 4*), follow-up of incident immunoglobulin users will start on the date of the first immunoglobulin prescription record of prespecified immunoglobulin brands during the study period. For primary care data sources, individuals are required to have 180 days data visibility prior to study inclusion and should not have a record of immunoglobulin prescription in the 180 days prior to study inclusion. For hospital care data settings, individuals are not required to have prior data availability, and no washout period will be applied prior to study inclusion. To ensure sufficient follow-up (*objectives 3–4*), only individuals with a first record of immunoglobulin prescription at least 180 days before the end of data availability in each data source will be included.

Follow-up (*objectives 1–4*) will end on the earliest of i) loss to follow-up, ii) death, iii) end of observation period (the latest available data), iv) or study end date 31/12/2024, whichever occurs first.

The code lists used to identify the start and end of follow-up determining events are presented in [Annex IV](#).

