#### *Objectives 3–4*

##### Inclusion criteria

- Present in the data source during the period of 01/01/2017 to 31/12/2024.
- Minimum 180 days of available history before index data. This criterion does not apply for hospital data source CDW Bordeaux.
- First drug prescription or dispensing record of prespecified immunoglobulin brand during the study period.
- No prior immunoglobulin exposure in the 180 days prior to the index date. This criterion does not apply for hospital data source CDW Bordeaux.

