  - Hepatology, including:
    - Hepatitis A
  - Other indications, which will be assessed overall and separately for each indication, where available, including:
    - Oncology
    - Autoimmune or paraneoplastic encephalitis
    - Epilepsy

- Progressive systemic sclerosis
  - Sjögren syndrome
  - COVID-19
  - Alzheimer
- Comorbidities: The top 10 most frequent diagnostic codes (comorbidities) will be identified through large-scale characterisation. These will be assessed 30 days prior to the index date [-30, 0], 1 year prior to the index date [-365, 0], and any time prior the index date [-inf, 0].

Common infections: Prespecified common infections among individuals initiating treatment with prespecified immunoglobulin brands will be assessed up to 30 days post-index [0, +30] and up to 365 days post-index [0, +365]. The following types of infections [4] will be assessed:

- Systemic infections, including:
  - Gram negative sepsis
  - Bacteraemia
- Bacterial infections, including:
  - Bacterial infectious disease
- Central nervous system infections, including:
  - Meningitis
- Respiratory & ear, nose, throat, ocular infections, including:
  - Otitis
  - Conjunctivitis
  - Bronchitis
  - Sinusitis
  - Respiratory tract infections
- Fungal infections, including:
  - Opportunistic mycosis
  - Invasive fungal infection
- Gastrointestinal & intra-abdominal infections, including:
  - Acute diarrhoea
  - Gastrointestinal infections
  - Peritonitis
- Urinary infections, including:
  - Urinary tract infections
- Viral infections:
  - Chronic enteroviral infections
  - Herpesvirus infections

- Antibiotic treatment: Exposure to prespecified antibiotics will be assessed up to 30 days post-index [0, +30] and up to 365 days post-index [0, +365]. The following classes of antibiotic ingredients will be assessed:
  - Tetracyclines
  - Amphenicols
  - Beta-lactam antibacterials, penicillins
  - Other beta-lactam antibacterials
  - Sulphonamides and trimethoprim
  - Macrolides, lincosamides, and streptogramins
  - Aminoglycoside antibacterials
  - Quinolone antibacterials
  - Other antibacterials

The preliminary concept sets used for the identification of covariates are described in [Annex IV](#). Final concept sets will be defined following input from EMA.

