To ensure comprehensive characterisation of all incident individuals, a minimum of 180 days of prior data availability is required for primary care data sources. This criterion may reduce the study size and will not be applied for hospital-based settings, where patients typically seek care for acute or specialised conditions and might, as a result, not have a long duration of longitudinal registration, as would be expected in a primary care setting data sources. Consequently, for CDW Bordeaux, it is uncertain whether included individuals are true incident users. Moreover, only a subset of included patients from hospital-based settings may contribute to time windows prior to the index date. The prior observation requirement may also imply selection bias favouring chronic indications, i.e., data in some pathological conditions may be limited or absent.

Of note, certain brands of interest cannot be assessed in the current study due to limitations, such as market authorisation occurring after the study period or the unavailability of an RxNorm code for those specific brands.

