#### **Germany: IQVIA Disease Analyzer Germany (IQVIA DA Germany)**

IQVIA DA Germany will be included in this study because it is a primary care data source that provides relevant information on the use of immunoglobulins in the general population.

Based on a preliminary feasibility assessment, the expected number of person counts for immunoglobulin use in IQVIA DA Germany will be 47,500.

Moreover, data availability and follow-up in IQVIA DA Germany is sufficient, as data availability starts in 1989, and the date of most recent data extraction 12/2024, which aligns with the study period. The median follow-up of the first observation period is 116 days.

There are no study specific limitations present in IQVIA DA Germany.

Lastly, IQVIA DA Germany requires no IRB approval, which makes the execution of this study feasible within the current study timelines.

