#### **United Kingdom: Clinical Practice Research Datalink GOLD (CPRD GOLD)**

CPRD GOLD will be included in this study because it is a primary care data source that provides relevant information on the use of immunoglobulins in the general population.

Based on a preliminary feasibility assessment, the expected number of person counts for immunoglobulin use in CPRD GOLD will be 73,600.

Moreover, data availability and follow-up in CPRD GOLD is sufficient, as data availability starts in 1987, and the date of most recent data extraction is 05/2025, which aligns with the study period. The median follow-up of the first observation period is 2,150 days.

There are no study specific limitations present in CPRD GOLD.

Lastly, CPRD GOLD has blanket approval, which makes the execution of this study feasible within the current study timelines.

Table S1. Fitness-for-use assessment of data sources.

Design elements	Operational definition	Data elements for valid capture	Criticality of the quality of the element, including justification where relevant	Suggested extensiveness assessment	Suggested assessment of other quality dimensions	Suggested substantiation by documentation
Study population	General study population ( obj. 1 )	N/A	N/A	N/A	N/A	N/A
	Population with an immunoglobulin prescription ( obj. 2–4 )	Prescription of immunoglobulin treatment (RxNorm code)	High	100% will have an immunoglobulin prescription, the expected number of persons counts for immunoglobulins in the data sources included in this study range from 10,900 (CDW Bordeaux) to 73,600 (CPRD GOLD).	100% of prescriptions have been mapped to RxNorm	N/A
Treatment/exposure	Immunoglobulin prescription	Prescription of immunoglobulin treatment (RxNorm code)	High	N/A (to be assessed on a research question basis)	N/A	N/A
Comparator group (not relevant)	N/A	N/A	N/A	N/A	N/A	N/A
Key outcomes per objective	Immunoglobulin prescription ( obj. 1 )	Prescription of prespecified immunoglobulin treatment (RxNorm code), including, if available, route of administration	Medium	Immunoglobulin prescriptions are included in all data sources. The expected number of persons counts for immunoglobulins in the data sources included in this study range from 10,900 (CDW Bordeaux) to 73,600 (CPRD GOLD).	N/A	N/A

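### The one-year comorbidity window is longer than the history that eligibility guarantees (180 days in primary care, none in CDW Bordeaux), so one-year proportions are likely understated by an unknown amount that may differ by source

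*Protocol*

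**What the plan says.** Section 8.6.3 of the protocol sets the comorbidity windows: "These will be assessed 30 days prior to the index date [-30, 0], 1 year prior to the index date [-365, 0"], plus any time before the index date. Section 8.8.3 repeats them and says that categorical characteristics are reported as counts and proportions. The Table 6 shell in section 8.8.4 prints n (%) for the ten most frequent conditions, by brand, with the three data sources side by side within each window.

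The eligibility criteria for objectives 3–4 in section 8.3 read: "Minimum 180 days of available history before index data. This criterion does not apply for hospital data source CDW Bordeaux". Section 8.2 confirms that in hospital data "individuals are not required to have prior data availability, and no washout period will be applied prior to study inclusion".

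Section 9 gives the reason for the requirement: "To ensure comprehensive characterisation of all incident individuals, a minimum of 180 days of prior data availability is required for primary care data sources". It then concedes that in hospital data only some patients may contribute to pre-index windows. It makes no such statement for the primary care sources. Section 9 also explains that people are observed from registration to deregistration in CPRD GOLD, from first to last recorded event in IQVIA DA Germany, and from first to last visit in CDW Bordeaux.

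**The concern.** The history requirement is presented as securing full characterisation, but it is about half as long as the one-year window it is meant to support, and no 180-day window is planned. A primary care initiator may enter with 180 to 364 days of history, and a CDW Bordeaux initiator with none. A condition recorded before observation began cannot be found for these people.

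If they remain in the denominator, the one-year proportion falls below what a full year of observation would show. If the share of such people differs between sources, part of any difference between the columns of Table 6 reflects look-back and not morbidity. A reader could then conclude that initiators in one country carry fewer comorbidities when they were only observed for less time. The any-time window has the same weakness. The [-30, 0] window does not in primary care, where 180 days cover it fully, but it does in CDW Bordeaux.

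**Working it through.** The study is descriptive and has no stated sample size, power or error rate to reproduce. The check compares the windows with the guaranteed history and then illustrates the size.

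**Inputs from the protocol**
- One-year window: 365 days before index, plus the index day (8.6.3).
- Guaranteed prior history: 180 days in IQVIA DA Germany and CPRD GOLD, 0 days in CDW Bordeaux (8.2, 8.3).
- Summary measure: n (%), with no denominator rule for a window observed only in part (8.8.3, Table 6 shell).

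**Step 1: guaranteed coverage**
- Primary care: 180/365 = 49.3%, leaving 365 − 180 = 185 days not guaranteed.
- CDW Bordeaux: 0/365 = 0%.

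**Step 2: who is in the denominator**
There are three possible rules.
- All initiators: people with incomplete look-back are included.
- Anyone observed at some point in the window: every window ends on day 0 and every initiator is observed on day 0, so this again includes everyone.
- Only people observed for the whole window: this removes the shortfall, but the protocol does not state it.

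So under the first two rules the one-year proportion is understated whenever some initiators have less than 365 days of history.

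**Step 3: illustration of size**
Assume that a condition is recorded at a constant rate, that a true proportion p would be seen over a full year, and that all initiators stay in the denominator. A person observed for exactly 180 days shows the condition with probability q = 1 − (1 − p)^(180/365). If a share f of initiators has exactly 180 days and the rest a full year, the reported proportion is (1 − f)p + fq.

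| True p | q | f = 10% | f = 25% | f = 50% | f = 100% |
|---|---|---|---|---|---|
| 10% | 5.1% | 9.5% | 8.8% | 7.5% | 5.1% |
| 20% | 10.4% | 19.0% | 17.6% | 15.2% | 10.4% |
| 40% | 22.3% | 38.2% | 35.6% | 31.1% | 22.3% |

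For CDW Bordeaux, take a share f observed on the index day only, so that q = 1 − (1 − p)^(1/366). With p = 20%, q is 0.06%, and the reported proportion is 18.0% (f = 10%), 15.0% (f = 25%) or 10.0% (f = 50%).

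The documents do not give f for any source, so no row or column of this illustration can be singled out as the expected result.

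**The case against.** Several points on the other side stand.

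- A reader might infer that the plan codes unobserved time as absence of disease. The protocol does not say so; it leaves the denominator open. The hospital sentence in section 9 could mean that only people observed in a window are counted. That reading does not remove the problem, because the index day lies in every window (step 2).
- A reader might take the Annex II medians as evidence that a full prior year is typical only in the UK: "The median follow-up of the first observation period is 116 days" for Germany against "The median follow-up of the first observation period is 2,150 days" for CPRD GOLD, with 247 days for CDW Bordeaux. These are figures for the whole source. A German patient with 116 days in total cannot meet the 180-day criterion, so the median does not describe the analysed cohort.
- A reader might expect a different top-10 list. Nothing in the documents shows that. The lists are ranked within source and brand, and under the constant-rate model the proportions shrink without changing order.
- The 180 days are a floor, and many initiators may have a full year. The case in which everyone sits at 180 days is a boundary, and the loss is smaller for chronic conditions that are coded repeatedly.
- The protocol gives none of the three windows priority. Results are presented by source without meta-analysis, section 9 already discloses the hospital part, and the Table 4 shell shows prior observation as a median with quartiles.

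Two things remain. The shortfall in primary care is not disclosed. The Table 4 quartiles also do not show how many initiators had 365 days, or what the proportion is among them.

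**Conclusion.** The concern holds in a limited form. The protocol pairs a 365-day window with guaranteed history of 49% of that window in two sources and 0% in the third, and it sets no full-window rule. One-year proportions are therefore likely understated in any source where some initiators have less than a year of history.

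The direction rests on partly observed initiators staying in the denominator. The size rests on their share, which is not given. That share probably differs by source, because observation periods are defined differently, but the documents do not establish which source is affected most or by how much. A reordering of the top-10 conditions is not shown either. The matter deserves a change because section 9 presents 180 days as sufficient and the table shell invites comparison across columns.

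**What to change.** 1. Add a [-180, 0] comorbidity window for IQVIA DA Germany and CPRD GOLD. Every included patient there satisfies it by design.
2. Keep the planned [-365, 0] result on all initiators, and say that this is the denominator. Beside it in Table 6, per source and brand, give the number with at least 365 days of prior observation and the proportion among them. For CDW Bordeaux, do the same for [-30, 0] with at least 30 days.
3. Extend the section 9 limitation to the primary care sources, and state that the one-year and any-time columns should not be compared across sources without the prior-observation figures.

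The cost is one additional window, one observation filter per supplementary result and extra columns in the shell. Numbers in the full-look-back subset will be smaller, and more cells may fall under the small-count suppression rule. The subset also favours returning or chronic patients, a selection that section 9 itself warns of for prior-observation requirements. It should therefore supplement the planned estimate and not replace it.

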The number of prescriptions, initial and cumulative dose of the index drug, as well as duration of use, will be provided per prespecified immunoglobulin brand as minimum, q25, median, q75, and maximum. For data sources where duration cannot be calculated, due to e.g., missing information on quantity or dosing, treatment duration will not be provided.

### Objective 4

Characteristics of individuals will be assessed in predefined time windows around the date of the first recorded prescription of immunoglobulins (index date) during the study period. For primary care data sources, a washout period of 180 days will be applied. Characteristics will be described for each prespecified immunoglobulin brand by means of large-scale characterisation and prespecified patient-level characteristics based on OMOP CDM mapped data using the *CohortCharacteristics* (<https://github.com/darwin-eu/CohortCharacteristics>) and *DrugUtilisation* (<https://github.com/darwin-eu/DrugUtilisation>) R packages, developed by DARWIN EU®.

Characteristics of interest will be reported as counts and proportions for categorical variables and as minimum, q25, median, q75, and maximum for continuous variables. Demographic characteristics, including age and sex, will be assessed at the date of first recorded prescription of immunoglobulins (index date) during the study period. Characterisation of prespecified indications for use will be assessed any time prior to 7 days after the index date, 30 days prior to 7 days after the index date, and 7 days prior to 7 days after the index date. Large-scale characterisation of comorbidities prior to immunoglobulin treatment will be assessed 30 days prior to the index date, 1 year prior to the index date, and any time prior to the index date. Characterisation of prespecified common infections and prespecified antibiotics treatment among immunoglobulin initiators will be assessed up to 30 days post-index and up to 365 days post-index.

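### The post-index infection and antibiotic windows include the index day, so events already present when immunoglobulin starts are reported as following initiation

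*Protocol*

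**What the plan says.** Under Objective 4, Section 8.8.3 places the assessment windows around "the date of the first recorded prescription of immunoglobulins (index date"), so day 0 is the day of the first immunoglobulin record.

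- **Infections** (Section 8.6.3): these "will be assessed up to 30 days post-index [0, +30] and up to 365 days post-index [0, +365".
- **Antibiotics** (Section 8.6.3): "Exposure to prespecified antibiotics will be assessed up to 30 days post-index [0, +30] and up to 365 days post-index [0, +365".
- **Comorbidities** (Section 8.6.3): "These will be assessed 30 days prior to the index date [-30, 0], 1 year prior to the index date [-365, 0". A third window takes in the whole recorded history up to and including day 0. Section 8.8.3 describes this part as "Large-scale characterisation of comorbidities prior to immunoglobulin treatment".
- **Indications** (Section 8.6.3): three windows, [-inf, +7], [-30, +7] and [-7, +7], all of which contain day 0.

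The column headers of mock Tables 6, 7 and 8 carry the same brackets, so a typing slip is unlikely. Objective 4 (Section 7) calls items iv and v post-index. No section excludes day 0 from any window, requires an infection to be new, or applies an infection-free period before the index date. Section 9 does not mention that the prior and post-index windows overlap.

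**The concern.** On the index day, the order of events is unknown. An infection coded that day may be the reason for the visit, an admission diagnosis or a finding made afterwards, and an antibiotic recorded that day may have been started before, with or after the immunoglobulin. Tables 7 and 8 would place all of these after initiation.

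This matters for how the tables will be read. Section 6 gives as background that restoring immunoglobulin levels can lower infection risk, so a reader will naturally take the proportions as infections and antibiotic use arising once treatment has begun. Part of each figure would instead describe the patient's state when treatment started.

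The comorbidity windows have the mirror problem: diagnoses coded on the index day are labelled as preceding treatment. Those codes can include the indication itself, because the top-10 list is selected by frequency and no removal of indication codes is stated.

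**Working it through.** **1. Day counts.** The brackets are closed intervals.

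| Window | As written | Without day 0 |
|---|---|---|
| Infections and antibiotics, short | [0, +30] = 31 days | [+1, +30] = 30 days |
| Infections and antibiotics, long | [0, +365] = 366 days | [+1, +365] = 365 days |
| Comorbidities, short | [-30, 0] = 31 days | [-30, -1] = 30 days |
| Comorbidities, one year | [-365, 0] = 366 days | [-365, -1] = 365 days |

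As written, the prior and post-index windows share exactly one day, day 0. An infection coded that day can count both as a prior comorbidity code and as a post-index infection. An indication coded that day can count both as an indication and as a comorbidity.

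**2. Direction.** Let A be a record on day 0 and B a record on days 1 to 30, with the same denominator throughout. The reported proportion is

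P(A or B) = P(B) + P(A) - P(A and B).

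The excess over P(B) is P(A without B), which cannot be negative. Including day 0 therefore leaves the proportion unchanged or raises it. The same holds for the 365-day window.

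**3. Size.** The protocol gives neither P(A) nor P(B). Assumed for illustration only: P(B) = 10%, P(A) = 5% to 20%.

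- Maximal overlap, P(A or B) = max[P(A), P(B)]: 10% when P(A) = 5%, and 20% when P(A) = 20%.
- Independence, P(A or B) = 1 - [1 - P(A)][1 - P(B)]: 1 - 0.95 × 0.90 = 14.5%, and 1 - 0.80 × 0.90 = 28%.

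A patient infected on day 0 is likely to be coded again within 30 days, so the truth should lie between these two cases: 10% to 28%, against 10% for days 1 to 30 alone. If no patient had both records, the sums would be 15% and 30%, but that is the least plausible pattern.

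**4. The hospital source.** Section 8.3 requires no prior history in CDW Bordeaux. Section 9 says that its patients are observed from first to last visit and that only some of them contribute time before the index date. For a patient first seen on the index date, each prior window holds day 0 only. For a patient last seen on that date, each post-index window holds day 0 only.

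**5. Would removing day 0 settle the comorbidity overlap?** No. An indication coded on day -10, say, still falls in [-30, -1], [-365, -1] and [-inf, -1]. A patient whose observation starts on the index date would have no comorbidity information at all.

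**The case against.** The strongest reply is that nothing is hidden. The brackets stand in Section 8.6.3 and above every column of the mock tables. The study is descriptive and tests no hypothesis (Section 8.7), it never calls these infections incident, and it plans no comparison of infection risk before and after treatment. That is right, and it rules out the inference that the figures are biased estimates of incidence or of a treatment effect: the protocol claims neither. What remains is a rule that, followed as written, reports index-day events under a label that says they came afterwards.

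Four further points stand and limit the concern:

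- **Antibiotics.** A course recorded on day 0 will normally give exposure on later days. Starting at day +1 without showing day 0 would undercount it.
- **Comorbidities.** A reader might infer that the indication will fill the top-10 lists. The documents support only that it may appear there, and ending the windows at day -1 would neither prevent this nor be free of cost in CDW Bordeaux.
- **Triple counting.** A reader might infer that one diagnosis is routinely counted as indication, comorbidity and post-index infection. Nearly all listed indications are non-infectious. Measles, hepatitis A and COVID-19 are the infectious ones, and the protocol does not show whether they fall under the listed infection concepts.
- **Re-coding.** An infection present at the start and coded again on day +1 or later would still count, so a window from day +1 is not an incidence measure either.

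**Conclusion.** The point holds for infections and antibiotics: the windows labelled post-index contain the index day, and the resulting proportions can only be equal to or higher than those for day +1 onward. That conclusion rests on the protocol's own brackets and needs no assumption beyond a common denominator.

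The size is not known. The 10% to 28% range depends entirely on the assumed 10% and 5% to 20% and on the degree of overlap; it shows that the effect could be anything from nil to a near tripling of the 30-day figure. That the effect is greatest in the 30-day window and in CDW Bordeaux is a reasonable inference, not a result.

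For comorbidities, the point is one of labelling and presentation. The windows are called prior but include day 0, and the top-10 codes may include the indication, whether it was coded on or before the index date. The change is worth making because Tables 7 and 8 are the only tables for Objective 4 items iv and v and would otherwise invite a wrong reading.

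**What to change.** - **Infections and antibiotics.** Report [+1, +30] and [+1, +365] in Section 8.6.3 and in Tables 7 and 8, and add a separate day-0 column to both tables. Same-day antibiotic starts then stay visible and no information is lost. State that the proportions are not incidence, because infections re-coded after day 0 still count.
- **Comorbidities.** Do not simply end the windows at day -1. Either give day 0 its own column in Table 6, or keep the windows and relabel them as prior to or on the index date in Sections 8.6.3 and 8.8.3 and in Table 6. Add a note that the top-10 codes may include the indication.
- **Section 9.** Add a sentence on how index-day records are handled.

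The cost is a change of window limits in the code, one extra column per data source in the affected tables, and a few words of text. The small downside is that an infection that truly began after treatment on the same day moves to the day-0 column.
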